Study participants who completed a psilocybin dosing session and agreed to be contacted in the future (as indicated on their written Informed Consent Document that was signed at the beginning of the primary phase of the study) will be approached by the study team member via phone or email to offer them participation in the optional, additional time points. If the study subjects are interested in participating in these two time points, a designated study-team member will read a telephone consent to the interested volunteer over the phone. The telephone consent discusses the additional study procedures that the volunteer would have to participate in and all risks involved. If the volunteer wants to participate in these optional and additional timepoints, a designated study-team member will send the interested participant a link to openredcap.nyumc.org. This link will include all of the assessments that are to be completed at each additional timepoint. The ability to complete these questionnaires online eliminates the need for the participant to come to an in-person visit at the study site. The T13 and T14 optional time points will occur approximately one year apart. The T13 time point will occur as soon as possible to the time at which verbal telephone reconsent is obtained, and the T14 will occur approximately one year after T13.

Because these timepoints are optional and participants only needed to undergo an active-medication session in order to be eligible, study participants who opt out or who do not have the option to participate (for example, if they are deceased) will be classified (ie study completers, withdrawn, treatment dropout, etc.) as they were in the main portion of the study

For example:

- Participant XYZ completed both medication sessions, active & placebo, as well as all questionnaire timepoints. He has been considered a “study completer” up until this point. If his consent endorses having the study team reach out to him regarding future research, he will be contacted. If he denies

wanting to participate in the optional & additional timepoints, this will not affect his status as a study completer.

- Participant ABC completed both medication sessions & all questionnaire timepoints but is deceased. She will still be considered a study completer even though she obviously cannot be given the choice to participate in T13 & T14.
- Participant LMN completed only 1 medication session but it was her active medication session. She withdrew from the study before her second medication session. However, since the protocol states that in order to be eligible for the optional & additional timepoints, participants must have only completed a psilocybin medication session, she would be eligible to participate in these additional and optional timepoints. If her consent endorsed having the study team reach out to her regarding future research, the study team will do so regarding these optional and additional questionnaire timepoints.

For documentation purposes, the study team will keep a log that includes all participants enrolled in the main portion of the trial and note whether or not they are deceased. Any and all information that the study team has regarding the death of a past participant in this trial will be noted.

Statistical Analyses (Including Power Analysis): Done in conjunction with [name] of Biostatistics and Approved on 1/24/07

Descriptive statistics (means, medians, standard deviations, frequency distributions) and graphic displays will be generated for demographics and baseline clinical presentations to characterize study subjects, and to describe the distribution of adverse events, patient dropout, study compliance and all outcome measures.

One of the objectives of this pilot study is to determine the feasibility of giving psilocybin to patients with advanced cancer. Although the safety of giving psilocybin to normal, healthy volunteers has been established within the last decade (Hasler 2004, Griffiths 2006, Moreno 1998), and although the safety of its use in patients with advanced cancer was established in the 1960s, it has not been established in patients with cancer using modern research designs (i.e. double-blind, placebo controlled, prospective methodology). In addition to safety determination considerations, summary statistics will be used to describe the consent and drop out rates as part of patient recruitment and retention. The adverse events associated with study treatments will be tabulated, and percent adverse event and its 95% confidence interval will be calculated.

According to a recent study by Moreno and colleagues, published in 2006, in patients with refractory Obsessive Compulsive Disorder (OCD), an anxiety spectrum disorder, it was found that, with psilocybin, subject's mean YBOCS scores were reduced to 10.67 at 24 hours from 24.11 +/- 6.3 at baseline (Moreno 2006). This represents a reduction of 2 in effect size (assuming a 0.5 correlation between baseline and 24 hours). If we assume placebo has no effect on anxiety, depression and pain, a sample size of 16 subjects in each group (in the first treatment session) will provide 75% power to detect a reduction of 1 effect size, and > 99% power at 2 effect sizes, at the 5% level. This power analysis shows that even if patients dropout before the second cross-over session, the total of 31 patients in the first session will have adequate power for the study endpoints.

Regarding the effect of psilocybin on the outcome variables measuring anxiety, the STAI and HAD scale, analyses will be conducted using a paired t-test to evaluate the effect of treatment over time. The comparisons will be between the following time points: (T0 & T1)-T4, (T0 & T1)-T5, (T0 & T1)-T6, and (T0 & T1)-T7. The comparisons between the active agent and placebo groups will be conducted using an independent sample t-test to look at differences on the STAI and HAD scale measures. Similar analyses will be conducted both within and between groups for the other outcome measures, assessing for depression (POMS-SR, BSI and BDI scales) and pain (BPI-SF, MSAS, and MSKCC scales).

To assess the interaction between drug and time, a series of repeated measures multivariate analyses of variance (MANOVA) will be used to compare the active drug and placebo study arms across time in terms of the major outcome variables during the first and second randomized experimental treatment sessions. Both treatment main effects across time and interactions of treatment with time will be assessed in the repeated measures MANOVA.

Longer-term effects will be measured in two ways looking at the outcome measures of anxiety, depression, and pain. First the effect of time will be assessed with a MANOVA analysis from baseline relative to T7-T12. Also, MANOVA will be used to look at the effect of sequencing of getting the active agent vs. placebo in a sequence x time analysis from baseline relative to T7-T12.

Data Management and Statistics:

A data manager will be recruited and appointed prior to the initiation of the study. The funding for this study from the Heffter Research Institute includes monies to pay for a data manager.

Monitoring for Risk Minimization:

A physical examination will be performed which will include an EKG, urinalysis, and blood chemistry panels (liver and renal function tests and CBCs). An admission urine drug screen will be done for patient safety and protocol compliance. During each experimental treatment session, vital signs, including blood pressure and heart rate, will be taken 10 minutes before and 30,60,90,120,180,240,300, and 360 minutes after drug administration. Body temperature will be measured up to 30 minutes before and at six hours after drug administration. For these measurements, a window of ± 10 mins from the allocated time will facilitate the study flow.

Cardiovascular monitoring during a session:

1. Vital Signs are checked ten minutes before and 30,60,90,120,180,240,300, and 360 minutes after capsule administration and monitor ratings (blood pressure and heart rate) will be serially assessed.
2. Monitor Ratings: Blood pressure (systolic, diastolic, and mean arterial pressure) and heart rate will be monitored with an automated blood pressure machine.
3. If Systolic BP is > 160 or Diastolic is > 100 or Heart Rate is > 110 , vital signs will be checked every 5 minutes until systolic pressure is < 160 , diastolic pressure < 100 , and heart rate < 110
4. If Systolic BP is > 200 or Diastolic BP is > 110 for three readings (i.e. 15 minutes), the subject will receive sublingual Nitroglycerin 0.4 mg. If blood pressure readings do not decrease below these thresholds after 5 minutes of receiving the first dose of Nitroglycerin, the same dose of Nitroglycerin will be administered. A third dose of nitroglycerin will be given after another 5 minutes, if readings remain elevated above these levels (maximum dose is 0.4mg x 3 doses).
5. If blood pressure remains > 200 systolic or > 110 diastolic, at the judgment of the treating physician ([name]), the subject will be immediately transported to the nearby Bellevue Hospital Center Adult Emergency Room (AES) for further evaluation and treatment.

Aversive reactions to sublingual nitroglycerin:

The following effects have occurred in clinical trials: headache, hypotension, cutaneous vasodilation with flushing, dizziness and weakness, as well as other signs of cerebral ischemia associated with postural hypotension. Also possible are nausea, vomiting, restlessness, pallor, perspiration and collapse, drug rash and/or exfoliative dermatitis, paresthesia, rhinitis, peripheral edema, asthenia, and abdominal pain.

PROCEDURE FOR MEDICAL EMERGENCIES:

NEW YORK UNIVERSITY COLLEGE OF DENTISTRY MEDICAL EMERGENCY MANAGEMENT PROTOCOL INCLUDING BLUESTONE CENTER FOR CLINICAL RESEARCH (BCCR):

The Department of Oral and Maxillofacial Surgery (OMS) faculty are trained in managing medical emergencies and will respond to the presentation of medical emergencies at the College of Dentistry.

In a medical emergency security will be called at [name] and they will dispatch the OMS faculty. Staff members who report the emergency must remain with the subject and administer supportive therapy. Emergency supplies and oxygen is available from the code cart located next to the nurse's station in BCCR.

The OMS team will assess the situation, stabilize the subject, and notify the Emergency Medical Service (EMS), should an ambulance be required to transport the subject to the hospital if this has not been done by BCCR staff. The OMS team will stay with the subject until the emergency has subsided or additional assistance has been obtained.

Other emergency numbers:

- Poison Control: [contact]
- Bellevue Emergency Room: [contact]
- New York University Emergency Room: [contact]

If an excessive rise in BP occurs, SBP >200 and/or DBP >140, it will be reported to the IRB and BCCR within 72 hrs. In addition the number of subjects in whom SBP >150 occurs will be reported as individuals in a special AE Table.

In the event that a subject experiences distressing anxious or psychotic symptoms during the experimental or control session, the clinical personnel in attendance (the principal investigator and treatment team) will initiate verbal communication designed to reorient and reassure the subject. If that does not effectively alleviate the signs of an anxious or psychotic reaction, a benzodiazepine (diazepam 5-10mg given orally or intramuscularly) will be administered to lower anxiety. Only if that is ineffective will an antipsychotic be administered, olanzapine (5-15mg given orally or intramuscularly).

Chemistry, manufacturing, and control information:

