It is hypothesized that a one time experience with psilocybin will occasion significant shifts in consciousness and awareness that will lead to short-term (i.e. hours to days) and long-term (up to 5 years in this study following the second experimental session) improvement in anxiety, depression, and pain associated with cancer. The exact mechanism of action is unclear but based on studies conducted with similar serotonergic agents in patients with advanced cancer, improvements in anxiety levels, mood and pain were reported (Grob and Halifax 1977; Kast 1970). However, a treatment model developed by the British psychiatrist, Humphrey Osmond, offers one possibility. In this model, serotonergic hallucinogens' therapeutic mechanism lies in their ability to allow the individual to access novel dimensions of consciousness and their efficacy or lack thereof relies on whether a significant reappraisal or alteration in perception is attained (Osmond 1957). Another possible mechanism relates to what Dobkin de Rios and Grob have described as 'managed altered states of consciousness,' where the power of suggestibility, occurring in a safe setting, allows one to transcend a particular state of consciousness (i.e. anxiety and depression associated with cancer) as a means to facilitate emotional discharge and to manage irreconcilable conflict (Dobkin de Rios, Grob, & Baker 2002).

Rationale and Background:

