This is a pilot study of a single treatment designed to preliminarily evaluate the effect of psilocybin in patients with cancer and anxiety. Secondary outcome measures will be pain perception, depression, and existential / psychospiritual distress. Also, issues related to the feasibility of using psilocybin in patients with cancer and anxiety will be described. The study will look at both short-term, immediate effects as well longer-term effects. We plan to collect and analyze data up to 6-months post the second drug administration for all enrolled participants. Participants who complete a psilocybin dosing session and agree to be contacted will be invited to partake in two optional data collection time points, which will look at long-term psychological effects of psilocybin-assisted psychotherapy.. Subjects’ participation in these two additional longitudinal timepoints will be optional and will not affect their previous study involvement as research participants. Study participants who opt out or who do not have the option to participate (for example, if they are deceased) will be classified (ie study completers, withdrawn, treatment dropout, etc.) as they were in the main portion of the study. Participants do not need to complete all questionnaires given at previous time points to be eligible to participate in optional time points T13 and T14.

Criteria for patient selection (Inclusion/Exclusion Criteria)

The proposed project will involve up to 47 subjects 18-76 years of age. Subjects will have a current or historical diagnosis of cancer with a projected life expectancy of approximately 6 months or more and a DSM-IV psychiatric diagnosis, as determined by the Structural Clinical Interview for DSM-IV (SCID), of one of the following Anxiety Disorders: Acute Stress Disorder, Generalized Anxiety Disorder, Anxiety Disorder Due to cancer, or Adjustment Disorder with Anxiety. The cancer could be: at any stage of active illness; potentially life

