In the first six weeks following the experimental treatment sessions, several follow-up meetings (at least 3 for a total minimum of 6 hours) in person between the subject, the study staff and the monitors will be arranged to facilitate psychological integration of the psilocybin experience, as well as to administer the research measures. Additional meetings in person or on the telephone will be held at least monthly intervals for further follow-up for six months. The principal investigator will be the primary contact person for the subjects.

Communication with community observers (i.e. family members, friends, co-workers) will be part of follow-up as a way to get an objective measure of patient outcome in addition to self-report.

Drug Conditions

Psilocybin and niacin will be administered in identically appearing opaque, size 0 gelatin capsules with approximately 180ml of water. The dose of psilocybin will be 0.3mg/kg and the niacin dose will be 250mg. Each subject will participate in two experimental treatment sessions. In the study, approximately half of the subjects will be randomized to receive psilocybin (n=15 or 16) or the placebo, niacin (n=15 or 16). Following

the first treatment session of either the active agent or placebo, a cross-over design will be instituted with the alternative drug administered on the second session. Subjects and treatment personnel will be blinded for each experimental drug administration. The time interval between the two experimental treatment sessions will be 7 weeks (+ 1 week).

For both experimental treatment sessions, patients will be weighed as close as possible to the day before the session, and the dose of psilocybin will be mixed and compounded the day prior to the drug administration session at 0.3mg/kg (- 4 day window). Regarding niacin, it too will be mixed and compounded the day before the drug administration session (- 4 day window).

Justification for 0.3mg/kg dose of psilocybin

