Treatment efficacy for anxiety and depression will be assessed by the State-Trait Anxiety Inventory (**STAI**), Hospital Anxiety and Depression (**HAD**) scale, Brief Profile of Mood States (**POMS-SR**), Beck Depression Inventory (**BDI**), and Brief Symptom Inventory (**BSI**). The STAI, HAD, POMS-SR, BDI, and BSI will also be re-administered at the following time points: T1, T4-T12. In addition, regarding a broad assessment of affective states, the Positive and Negative Affect Schedule Expanded Form (**PANAS-X**), a 60-item questionnaire, will be administered to assess for positive and negative affect. This scale will be re-administered at the following time points: T6 (2-weeks after drug administration) and T12 (26-weeks after drug administration). The STAI, HAD and BDI will be re-administered at T13 and T14.

Pain

Treatment efficacy for pain perception will be assessed by the Brief Pain Inventory – Short Form (**BPI-SF**), and the Memorial Symptom Assessment Scale (**MSAS**) (only questions relevant to anxiety, depression or pain symptoms) will be administered two weeks prior to the experimental treatment session, the day before, 7-hours after each drug administration session, the day after, two weeks after the session, and then every month for the next six months. In addition, the Memorial Sloan Kettering Pain Card (**MSKCC**) will be self-administered by the subjects every day from two weeks before the treatment session until six weeks after, including just before psilocybin administration and at four and seven hours afterward. Subjects' use of pain medications will be closely monitored throughout the study duration.

Attitudes towards disease progression and death

Attitudes towards disease progression and death will be measured at baseline with the following measures: Death Transcendence Scale (**DTS**), Demoralization Scale (**DEM**), Death Anxiety Scale (**DAS**), and the Hopelessness Assessment and Illness (**HAI**) scale. These measures will also be obtained at the following time points: T6 (2-weeks after drug administration) and T12 (26-weeks after drug administration). The DEM, DAS and HAI will be re-administered at T13 and T14.

Quality of Life/Spirituality:

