Regarding the assessment of enduring changes in attitudes and affect, the Persisting Effects Questionnaire (**PEQ**), an 89-item questionnaire, will be administered to assess changes in attitudes, moods, behavior, and spiritual experience (Pahnke 1969; Richards 1977). The categories of inquiry from this questionnaire include: positive attitudes about life and/or self, negative attitudes about life and/or self, positive mood changes, negative mood changes, altruistic/positive social effects, and antisocial/negative social effects. In addition, regarding a broad assessment of affective states, the Positive and Negative Affect Schedule Expanded Form (**PANAS-X**), a 60-item questionnaire, will be re-administered.

Measures relating to quality of life, spirituality and forgiveness will be re-assessed with the FACIT, PIL, WHO-Bref, WHO-SPRB, and the Forgiveness Questionnaire.

The Kast questionnaire will be re-administered to assess for the quality of the drug administration experience.

The DTS, DEM, DAS, and HAI will be re-administered to assess for attitudes towards disease progression and death.

Measures assessed 6 weeks after drug administration (T₇):

The STAI, HAD, POMS-SR, BDI, and BSI will be administered to assess for anxiety and depression, and the BPI-SF, MSAS, and MSKCC will be administered to assess for pain.

Regarding community observer ratings of changes in subjects' behavior and attitudes, the above-mentioned structured interview (COM-R) will be re-administered.

Measures assessed 10 weeks after drug administration (T₈):

The STAI, HAD, POMS-SR, BDI, and BSI will be administered to assess for anxiety and depression, and the BPI-SF, and MSAS, will be administered to assess for pain.

Measures assessed 14 weeks after drug administration (T₉):

The STAI, HAD, POMS-SR, BDI, and BSI will be administered to assess for anxiety and depression, and the BPI-SF, and MSAS, will be administered to assess for pain.

Measures assessed 18 weeks after drug administration (T₁₀):

The STAI, HAD, POMS-SR, BDI, and BSI will be administered to assess for anxiety and depression, and the BPI-SF, and MSAS, will be administered to assess for pain.

Measures assessed 22 weeks after drug administration (T₁₁):

The STAI, HAD, POMS-SR, BDI, and BSI will be administered to assess for anxiety and depression, and the BPI-SF, and MSAS, will be administered to assess for pain.

Measures assessed 26 weeks after drug administration (T₁₂):

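### Visits T8–T12 appear to run from the second session whichever drug was given, so the long-term MANOVAs mix, or confound with sequence, two lengths of time since psilocybin

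*Combined protocol and SAP*

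**What the plan says.** - **Visit labels.** In Observations and Measurements, visits are labelled by time since drug administration, without saying which of the two. PANAS-X, for example, is repeated at "T6 (2-weeks after drug administration) and T12 (26-weeks after drug administration". The T8 heading is "Measures assessed 10 weeks after drug administration".
- **End of follow-up.** Objectives and Purpose of the Study: "We plan to collect and analyze data up to 6-months post the second drug administration for all enrolled participants". The Hypothesis section also counts long-term benefit from session 2: "up to 5 years in this study following the second experimental session".
- **Design.** Drug Conditions: "a cross-over design will be instituted with the alternative drug administered on the second session", and "The time interval between the two experimental treatment sessions will be 7 weeks (+ 1 week". On allocation, "approximately half of the subjects will be randomized to receive psilocybin (n=15 or 16) or the placebo, niacin (n=15 or 16".
- **Long-term analysis.** Statistical Analyses plans two analyses of anxiety, depression and pain. For the first, "First the effect of time will be assessed with a MANOVA analysis from baseline relative to T7-T12"; no sequence term is named. The second is a sequence-by-time MANOVA over the same visits. Neither uses time since psilocybin.

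**The concern.** The durability question is how long benefit lasts after psilocybin. If the clock starts at session 2 for everyone, it starts at psilocybin in one sequence and at niacin in the other. A visit with one label then stands for two lengths of follow-up.

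Two results are exposed. An average over all patients at T12 is not a 26-week result for psilocybin. And if benefit wanes, psilocybin-first patients will look worse than niacin-first patients at the same visit simply because they are further from the drug. That pattern could be taken for an effect of treatment order.

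**Working it through.** **1. Which session anchors T8–T12?** T12 is at 26 weeks. 26 × 7 / 30.44 = 5.98 months, which matches follow-up to six months after the second administration. T8 is at 10 weeks, and session 2 comes 7 to 8 weeks after session 1, so T8 onward cannot be a first-period series free of the crossover. Both facts point to session 2. This is an inference, since no visit heading states it.

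**2. Weeks since psilocybin.** Niacin-first: the visit week. Psilocybin-first: the visit week plus the gap of 7 to 8.

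| Visit | Psilocybin-first | Niacin-first |
|---|---|---|
| T7 after session 2 (week 6) | 13–14 | 6 |
| T8 (week 10) | 17–18 | 10 |
| T9 (week 14) | 21–22 | 14 |
| T10 (week 18) | 25–26 | 18 |
| T11 (week 22) | 29–30 | 22 |
| T12 (week 26) | 33–34 | 26 |

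**3. What a pooled T12 represents.** With 31 patients split 15/16, the mean time since psilocybin runs from (15 × 33 + 16 × 26)/31 = 29.4 weeks to (16 × 34 + 15 × 26)/31 = 30.1 weeks. Neither sequence is measured at that time.

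**4. The alternative anchor.** Counting T12 from session 1 gives 26 weeks for psilocybin-first and 26 − 8 = 18 to 26 − 7 = 19 weeks for niacin-first. The offset is the same, and follow-up would stop 18–19 weeks after session 2, short of the stated six months.

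**5. Possible size.** The documents give no rate of change, so the half-lives h below are assumptions. Take the remaining effect as 0.5^(w/h) at w weeks, a mid-range offset of 7.5 weeks, equal sequences and no true order effect.

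- At T12 with h = 26: psilocybin-first 0.5^(33.5/26) = 0.409, niacin-first 0.500, pooled 0.455. The shortfall against a true 26-week effect is 0.045 of the initial effect, or 9% of what remains.
- At T8 with h = 13: 0.5^(17.5/13) = 0.393 against 0.5^(10/13) = 0.587, a gap of 0.19 of the initial effect.

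| Assumed half-life | T12 shortfall, share of remaining effect | T12 shortfall, share of initial effect | T8 sequence gap, share of initial effect |
|---|---|---|---|
| 13 weeks | 16% | 0.041 | 0.19 |
| 26 weeks | 9% | 0.045 | 0.14 |
| 52 weeks | 5% | 0.034 | 0.08 |
| No change | 0 | 0 | 0 |

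**The case against.** **The plan does not only pool.** A reader might infer that the sequences are never separated. That is wrong: the sequence-by-time MANOVA does so. It still compares them at the same nominal visit, so it does not remove the 7–8 week difference in time since psilocybin.

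**The anchor is inferred.** The text refers to a Table 1 that is not in the material available for review and may define the anchor. This stands, so naming the anchor is part of the fix. Either anchor leaves two follow-up lengths.

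**The T12 label also covers scales outside these analyses.** The long-term MANOVAs are described for anxiety, depression and pain. A reader might infer that a pooled 26-week result is planned for attitudes, quality of life, spirituality, PANAS-X, PEQ or the community-observer ratings. Statistical Analyses names none. Nor are these scales measured only at T12, because each is also given at T6 or T7. For them the point is one of reporting.

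**The numerical effect may be small.** Take a unit SD and the 1 to 2 effect sizes of the power section. The assumed half-lives then give a T12 shortfall of about 0.03 to 0.09 SD, against a standard error near 1/√31 = 0.18. At 1 effect size the T8 gap is 0.08 to 0.19 SD, against √(1/15 + 1/16) = 0.36. No figure in the documents shows waning, and the hypothesis is of lasting benefit. This stands as a limit on size. It does not make the time label right.

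**Realignment has its own confounding.** Matching on time since psilocybin misaligns time since baseline. That stands and is carried into the fix.

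**Conclusion.** The point holds for the long-term analyses. On the best reading of the text, each visit from T8 to T12, and T7 if taken after session 2, falls 7–8 weeks later after psilocybin in psilocybin-first than in niacin-first patients; T12 is 33–34 against 26 weeks. The time MANOVA as written mixes these lengths. The sequence-by-time MANOVA cannot tell an order effect from waning.

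The week counts follow from the stated gap once session 2 is accepted as the anchor. The size of any bias does not: it rests on assumed half-lives and is nil under a plateau.

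A reader might infer that the main drug-versus-placebo result is compromised. The documents do not support that, because the first-session comparisons through T7 are made before the crossover and are unaffected. This is an inexpensive improvement worth making to the secondary, long-term part of a pilot.

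**What to change.** 1. State the anchor session for each of T6 to T12.
2. Keep both planned MANOVAs. Add a long-term analysis of anxiety, depression and pain with weeks since psilocybin as the time variable and sequence as a term. The scheduled visits match to within a week at these points:
   - week 6: T7 after the psilocybin session in each sequence;
   - week 14: psilocybin-first T7 after session 2 with niacin-first T9, if T7 is done after both sessions;
   - weeks 18, 22 and 26: psilocybin-first T8, T9 and T10 with niacin-first T10, T11 and T12.
3. Do not read a sequence-by-time difference at one nominal visit as an order effect without this analysis.
4. For scales whose only measurement within T8–T12 is T12 (attitudes, quality of life, spirituality, PANAS-X, PEQ, community-observer ratings), report T12 by sequence with the actual time since psilocybin, 33–34 against 26 weeks.

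**Cost.** Analysis-plan wording and relabelled visits; no new data. Matching on time since psilocybin shifts time since baseline, and at the later points time since the last session, by about 7–8 weeks between sequences. The sequence term would carry those differences along with any order effect, so results by sequence must still be shown. Niacin-first T8 (week 10) and psilocybin-first T11–T12 have no partner and stay descriptive.
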